### 3.3. C.4.d. Diagnostic and Clinical Rating Assessments

Raters (MD or PhD level) experienced with the assessment of SAD will conduct clinician assessments. Independent evaluators blind to randomization assignment will conduct the primary symptom severity outcome measure (LSAS) and other outcomes. Reliability will be established by joint ratings prior to study initiation and repeated at 6-month intervals during the study to minimize drift.

**MINI International Neuropsychiatric Interview** (MINI, screening only). This structured diagnostic interview will establish DSM-5 diagnoses for eligibility assessment.

**Liebowitz Social Anxiety Scale – Self-Rated** (LSAS-SR, screening only) 24-item self-rated assessment of social anxiety symptom severity, well validated.

**Hamilton Rating Scale for Depression**, 17-item (HRSD, screening and weeks 0,2,4,8, 3-month follow-up)

**Columbia Suicide Severity Scale** (screening and as-needed) will be used for screening and to assess an suicidal ideation occurring during participation.

Outcome measures at weeks 0,2,4,8, 3-month follow-up:

**Liebowitz Social Anxiety Scale – Clinician-Rated** (LSAS) Widely used and well validated 24-item assessment of severity of symptoms of SAD.

**Social Phobia Inventory (SPIN)** – Validated self-rating assessment of severity of symptoms of SAD.

**Quality of Life Enjoyment and Satisfaction Questionnaire (QLESQ)** – Self-rated scale for quality of life.

**Revised Social Anhedonia Scale** – 15-item self-rated scale derived from Chapman Social Anhedonia Scale, with superior discrimination of social anhedonia from social anxiety.

**Post-treatment Debriefing Questionnaire** – This self-rated form will assess the participant's experience of GC-MRT, including treatment acceptability (using a modified version of the **Client Satisfaction**

**Questionnaire**), and awareness of the reward contingency.

**Randomization Method (R61 and R33).** We will use stratified randomization to assign subjects into two randomized groups. Strata will be defined based on baseline medication use (yes/no). Forty subjects will be randomized in the R61 phase to two dosage groups,

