### 3.3. C.5 Data Analysis and Hypothesis Testing

All quantitative measures will be graphed by group and checked for outliers and inconsistent values. If a variable has many outliers or shows heteroscedastic behavior (i.e., unequal variances), we shall consider transformations using a power function. Any remaining outliers will be winsorized (i.e., censored down to the nearest non-outlier value). Missing values. Missing values on outcome measures will be summarized by randomization group. We will test for differential missingness between groups. We will use mixed effect models for the statistical analyses, as these can analyze data with ignorable missingness (missing at random). G\*Power 3.1. and the R library longpower were used to calculate statistical power.

**R61.** Forty adults with SAD will be randomized to standard GC-MRT (8 sessions in 4 weeks) or extended GC-MRT (8 sessions in 12 weeks), with the target of attention allocation assessed at each session. **Aim 1:**

Hypothesis 1: *The target measure (% dwell time on threat faces) will decrease significantly during GC-MRT.*

The primary analysis will be intention-to-treat using a mixed effect model with change in % dwell time from baseline to the repeatedly measured outcome from all sessions after session 3 in both groups, using categorical time and baseline % dwell time as fixed effects, with an AR(1) correlation structure within subjects. The effect of interest will be the intercept, as this is a pooled analysis that does not differentiate between randomization groups or time points. A secondary analysis will use data from all sessions to test the categorical time effect predictor's effect, to identify time points with significant mean change scores adjusting for baseline medication use (yes/no). Additionally, the completer analysis will be a matched pair t-test of pre-post % dwell time values. Power Analysis: For the completer analysis, our already published data lead us to expect an effect size for reduction in the % dwell time of at least Cohen's  $d = 0.68$ . Assuming a 10% dropout with  $N=40$  enrolled subjects, and a 0.05 significance level, we will have at least 98% power to detect this change, with  $d = 0.48$  the minimum detectable effect size. For the repeated measures analysis, with within-subject autocorrelation parameter  $r = 0.6$ , we will have at least 80% power to detect an effect size of  $f = 0.17$ ,

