corresponding to  $d = 0.34$ , while with  $r = 0.2$ , the minimal detectable effect size is  $f = 0.23$  or  $d = 0.45$ . In either case, the power for  $d = 0.68$  will be  $>99\%$ .

**Aim 2: Hypothesis 2:** *Eight weeks after starting treatment, mean Liebowitz Social Anxiety Scale (LSAS) total score will be significantly lower in the 8-week treatment group than in the 4-week group.* We will use a t-test for the change score at 8 weeks after starting treatment for completers. We will also compare groups on % dwell time at last session but do not expect a group difference. Power Analysis. We do not have preliminary data for the 8-week dose of treatment. For the two-group t-test, with  $n=20$  per group enrolled, and 18 per group completers (10% dropout), we will have 80% power to detect an effect of size  $d=0.96$  or larger. Thus we will be able to detect large effect sizes for the dosage difference. However, dose selection for the R33 will not require statistically significant superiority (see criterion for selecting dose, below).

**Aim 3 (Exploratory):** (See below for processing MRI and tasks data) We will test the association between change in attention control and reward processing and change in % dwell time by Pearson correlation coefficients. *We will also explore predictors of target engagement (baseline attention allocation and neural activation), to advance personalized treatment.* We will fit mixed effect regression models as described in Hyp 1, with repeatedly measured reduction in % dwell time as outcomes, with the predictors listed above.

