**R61 Go-Nogo Criterion:** Mean % dwell time on threat faces during the last session of the 8-session or 12-session treatment will decrease by more than 7.2 percentage points relative to baseline, corresponding to a medium effect size of Cohen's  $d=0.48$ , based on preliminary data. We have  $>80\%$  power to detect this difference under all scenarios. Clinical significance of cutoff: Based on preliminary data, since % dwell time reduction will partially mediate clinical symptom reduction, this effect corresponds to symptom reduction of  $d = 1.34$ , corresponding to 21.3 points on the LSAS scale. **R61 criterion for selecting dose for the R33:** If only one dosage group passes the Go-Nogo Criterion, that dose will be selected for the R33. If both dosage groups satisfy the Go-Nogo Criterion, we will decide based on the following: If improvement (decrease) in LSAS total score 8 weeks after starting treatment is at least 7 points greater in the 12-session/8-week treatment group than in the 8-session/ 4-week treatment group, we will use the 8-session/12-week treatment in the R33.

**Aim 4: Hypothesis 3:** *Compared to control treatment, GC-MRT will significantly improve symptoms (LSAS) & QoL (Quality of Life Enjoyment & Satisfaction Scale, QLESQ: a) at post-treatment and b) at 3-month follow-up.* As primary analysis, we will use a two-sample t-test for the LSAS change scores at the last session in completer subjects. For the 3-month follow-up, a similar analysis will be performed. Secondary analysis will be similar analyses of the QLESQ, and a mixed effects model of each outcome with change score (relative to baseline) as the outcome, and randomization group, time point, and the baseline score as the predictors. Power Analysis. We assume 10% drop-out in each group. From our preliminary data analysis, expected effect size for reduction in LSAS for completer subjects, compared to controls, will be  $d = 1.35$ . Using a two-sample t-test, with Bonferroni-corrected 0.025 significance level, we will have 99% power to detect this. We do not have preliminary data for the QLESQ; the minimal detectable effect size for the change difference will be  $d=0.74$ , a moderate effect size.

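### The between-dose comparison of last-session % dwell time should be a baseline-adjusted difference with a 95% CI, because at about 18 per arm a non-significant result would not show similar target engagement

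*Combined protocol and SAP*

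**What the plan says.** All references are to the combined protocol and SAP.

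- **Section 3.3. C.5, Aim 2.** Hypothesis 2 is about LSAS: a difference between the two dose groups eight weeks after starting treatment, tested by a t-test on change scores in completers. The target measure gets one sentence: "We will also compare groups on % dwell time at last session but do not expect a group difference".
- **Same paragraph, power.** With 20 enrolled and 18 completing per group, "we will have 80% power to detect an effect of size $d=0.96$ or larger". The plan adds that this allows large dosage effects to be detected. The power statement follows the LSAS test; none is given for % dwell time.
- **Section 3.3. C.5, Aim 1.** The primary analysis of % dwell time pools the dose groups and has baseline % dwell time as a fixed effect. A secondary analysis adjusts for baseline medication use.
- **Section 3.3. C.4.a.** Baseline % dwell time is the average over the first five matrices of Session 1. Each session score averages 30 matrices.
- **Randomization Method (section 3.3. C.4.d).** Randomization is stratified by baseline medication use.
- **R61 Go-Nogo Criterion and dose selection.** The Go-Nogo criterion is a decrease from baseline of more than 7.2 percentage points, given as d = 0.48. If both doses pass, a 7-point difference in LSAS improvement guides the choice.

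**The concern.** The Aim 2 sentence is the only between-dose contrast on the target that section C.5 describes. Its predicted result is a null, and the plan gives no interval, margin or reading rule. As written, the only way the comparison can appear to bear out the expectation is by failing to reach significance, and a small comparison will often do that whatever the truth.

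What is at stake is interpretation. Aim 2 predicts an LSAS difference alongside no dwell-time difference, while the Go-Nogo text says that dwell-time reduction partly mediates symptom reduction. If R61 found an LSAS advantage and a non-significant dwell-time comparison, it would be natural to write that the extra sessions help by some route other than the target. Whether the data could bear that statement depends on how precisely the dwell-time difference is estimated.

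The wording also describes a comparison at the last session without mentioning each patient's baseline, although the baseline is collected and is used in Aim 1.

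**Working it through.** **Inputs**

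| Input | Value | Source |
|---|---|---|
| Patients per arm | 18 (20 less 10% dropout) | Aim 2, stated for LSAS; carried over to % dwell time here |
| Test | two-sample t-test | Aim 2, stated for LSAS; carried over |
| Alpha | 0.05, two-sided | 0.05 is stated under Aim 1; two-sided is inferred because it reproduces the Aim 2 figure |
| SD of % dwell time | 15 points | 7.2 / 0.48, from the Go-Nogo Criterion; assumed to apply to the compared score |
| Difference examined | 0.5 SD | illustrative, not a figure in the plan |

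**1. Reproduce the plan's figure.** For n per arm, the noncentrality is d × √(n/2), with 2n − 2 degrees of freedom. At n = 18, √(18/2) = 3, df = 34 and the critical t is 2.032.

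- d = 0.96: noncentrality 2.88, power 79.9%. Solving for 80% power gives d = 0.961, so the plan's figure is confirmed.
- A one-sided test would give d = 0.85, and 20 per arm would give d = 0.91. Neither matches, so two-sided with 18 per arm is the plan's basis.

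**2. Apply the same test to % dwell time, unadjusted.**

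| True difference (SD) | Noncentrality | Power | Chance of a non-significant result |
|---|---|---|---|
| 0.3 | 0.90 | 14% | 86% |
| 0.5 | 1.50 | 31% | 69% |
| 0.8 | 2.40 | 65% | 35% |

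If all 20 per arm gave data, power at 0.5 SD would be 34%.

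**3. Precision.** The 95% half-width is t × √(2/n) = 2.032 × √(2/18) = 2.032 × 0.333 = 0.68 SD.

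- At SD 15: standard error 15 × 0.333 = 5.0 points, half-width 2.032 × 5.0 = 10.2 points.
- For an assumed SD of 10 to 20: half-width 6.8 to 13.6 points.

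An observed difference of exactly zero would thus still be compatible with true differences of up to about 0.68 SD in either direction.

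**4. What baseline adjustment gains.** With correlation r between baseline and last-session dwell time, the standard error is multiplied by about √(1 − r²).

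- r = 0.3: factor 0.95, about 5% smaller. At SD 15 the half-width is about 10.2 × 0.95 = 9.7 points.
- r = 0.7: factor 0.71, about 29% smaller. The half-width is about 10.2 × 0.71 = 7.2 points.
- Power at 0.5 SD is about 32% for r = 0.2 and 45% for r = 0.6.

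The documents give no value for r, so the range is assumed. The baseline rests on five matrices against 30 for a session score, so it is the noisier measure and r may be modest.

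**The case against.** The strongest reply is that the plan does not contain the faulty inference. Three stronger readings are tempting, and the documents support none of them.

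- **That the plan claims or tests equivalence.** It does not. It states an expectation about a secondary comparison and says nothing about how a non-significant result will be read. Hypothesis 2 concerns LSAS only.
- **That the dose decision is at risk.** It is not. Dose selection uses each arm's own Go-Nogo result and then the LSAS difference, and Aim 2 says that statistically significant superiority is not required.
- **That the comparison should be judged against ±7.2 points.** That threshold is a within-group decrease from baseline, and the plan nowhere presents it as a meaningful difference between doses. At SD 15, the reduction expected under Aim 1 (d = 0.68) is about 0.68 × 15 = 10.2 points, so a 7.2-point gap between doses would be about 70% of the whole expected effect. At 18 per arm and SD 15, an unadjusted equivalence test with that margin would pass less than 1% of the time even with no true difference.

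It is also fair to say that the plan discloses its limits, since the same paragraph speaks of detecting large dosage effects. The absence of baseline adjustment is likewise read from silence: section C.5 says generally that mixed effect models will be used, and the Aim 1 model includes baseline dwell time.

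All of this stands and makes the point small. It does not remove it. The sentence leaves the estimator and the reading of its predicted null open, and even with adjustment at r = 0.6 a 0.5-SD difference would be missed about 55% of the time.

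**Conclusion.** The point holds as a minor, cost-free improvement to the analysis and its reporting. It is not an arithmetic error, since the plan's d = 0.96 reproduces.

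If the last-session comparison is an unadjusted two-sided t-test with about 18 per arm, power is about 31% for a 0.5-SD difference and the 95% CI half-width is about 0.68 SD, or roughly 10 points at SD 15. A non-significant result would not show similar target engagement at the two doses.

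This rests on three assumptions:

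- The test and the 18 per arm carry over from the LSAS analysis.
- 0.5 SD is an illustrative size.
- The 15-point SD comes from an effect size for change from baseline and may differ from the SD of last-session values. The results in SD units do not depend on it.

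**What to change.** Replace the Aim 2 sentence on % dwell time with wording such as:

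> The between-dose difference in last-session % dwell time will be estimated from a model adjusting for baseline % dwell time and the medication-use randomization stratum, and reported with its 95% confidence interval. A non-significant difference will not be taken as evidence that the doses engage the target equally.

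The plan should also state the analysis set and expected number per arm for this comparison, and note that precision is limited at about 18 per arm.

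Do not add a ±7.2-point equivalence margin. If the investigators later wish to claim similarity, they would need a between-dose margin justified in its own right, and this sample is unlikely to be large enough to meet a tight one.

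The cost is SAP wording only. Baseline dwell time comes from Session 1 and medication use is recorded for stratification, so no new data or patients are needed. The one consequence to accept is that the expected finding of no difference will probably be reported as an imprecise estimate.

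### The power figure of more than 80% attached to the R61 Go/No-Go criterion belongs to the whole-sample Aim 1 tests against zero change and is not the chance of passing the gate

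*Combined protocol and SAP*

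**What the plan says.** All of this is in the combined protocol and SAP, section 3.3. C.5.

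- **The gate (R61 Go-Nogo Criterion).** The criterion is set on the average share of gaze time spent on threat faces, with this timing and cutoff: "the last session of the 8-session or 12-session treatment will decrease by more than 7.2 percentage points relative to baseline". The plan equates this cutoff to d = 0.48 and adds that there is more than 80% "power to detect this difference under all scenarios". It names no test or sample size for the gate and does not list the scenarios.
- **The dose rule (same section).** "If only one dosage group passes the Go-Nogo Criterion, that dose will be selected for the R33". The LSAS comparison comes in only afterwards: "If both dosage groups satisfy the Go-Nogo Criterion, we will decide based on the following".
- **The dwell-time power work (Aim 1, Hypothesis 1).** For the completer test the plan expects at least d = 0.68. With N = 40 and 10% dropout it says: "and a 0.05 significance level, we will have at least 98% power to detect this change". It gives d = 0.48 as the minimum detectable effect. For the repeated-measures model the detectable effects are d = 0.34 (r = 0.6) and d = 0.45 (r = 0.2). Of that model the plan says that "this is a pooled analysis that does not differentiate between randomization groups or time points".
- **Group size and expected group difference (Aim 2).** Each group has 20 enrolled and 18 completers. On dwell time: "We will also compare groups on % dwell time at last session but do not expect a group difference".

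**The concern.** The sentence sits inside the Go/No-Go criterion, so it reads as the reliability of the decision that opens R33 and may fix its dose. It appears to have been carried over from Aim 1, which asks a different question of a different sample. Aim 1 asks whether the mean change in the whole sample differs from zero. The gate asks whether an observed mean exceeds 7.2 points, and the dose rule asks this of each half of the sample. Power against zero does not give the chance of clearing a cutoff set at the assumed effect itself. In the text reviewed, this is the only reliability figure given for the gate.

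**Working it through.** **Inputs.** From the plan: cutoff 7.2 points, d = 0.48 at the cutoff, expected d = 0.68, alpha 0.05, 40 enrolled with 10% dropout (36 completers), and 20 enrolled or 18 completers per group. Assumed: SD of change = 7.2/0.48 = 15 points, since the plan does not state the SD. This takes d as mean change divided by SD of change. The expected drop is then 0.68 × 15 = 10.2 points.

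**Step 1: reproduce the plan's figure.** For a paired t-test with n = 36, the noncentrality is d√n.

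- d = 0.68: 0.68 × 6 = 4.08, two-sided power 97.8% (plan: 98%).
- d = 0.48: 0.48 × 6 = 2.88, two-sided power 79.96%. The effect detectable with 80% power is 0.480, as the plan states.
- A one-sided test would give 88.1% at d = 0.48, but a detectable effect of 0.42, which does not match the plan. The two-sided reading is therefore the one that fits.

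The repeated-measures detectable effects (0.34 and 0.45, taken as stated) are both below 0.48. The sentence therefore fits the three Aim 1 settings, except that the completer test is at about 80% and not above it.

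**Step 2: the chance of passing the gate.** For one group, p = Φ((true drop − 7.2)/(SD/√n)). For two independent groups with the same true drop, at least one passes with probability 1 − (1 − p)², both with p², and exactly one with 2p(1 − p).

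*True drop 7.2 points.* The numerator is zero, so p = 50% at any n and SD, per group or pooled. At least one: 1 − 0.5² = 75%. This needs only a roughly symmetric sampling distribution of the mean.

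*True drop 10.2 points, SD 15, n = 18.* The standard error is 15/√18 = 3.54, and 3.0/3.54 = 0.85, so p = 0.802.

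| True drop | n per group | Each group | At least one | Both | Exactly one |
|---|---|---|---|---|---|
| 7.2 (d = 0.48) | any | 50% | 75% | 25% | 50% |
| 10.2 (d = 0.68) | 18 | 80% | 96% | 64% | 32% |
| 10.2 (d = 0.68) | 20 | 81% | 97% | 66% | 30% |

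Simulation with n = 18 at the 10.2-point drop gave the same four values (0.802, 0.961, 0.643, 0.318).

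**Step 3: sensitivity of the exactly-one figure, n = 18.** At a fixed 10.2-point drop it is 18% for SD 10, 25% for SD 12, 32% for SD 15 and 36% for SD 18. At SD 15 it falls to 16% for d = 0.80 (12.0 points) and 7% for d = 0.90 (13.5 points).

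**Step 4: drop needed for an 80% pass chance in one group.** 7.2 + 0.8416 × 15/√18 = 10.2 points, that is d = 0.68.

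**Step 5: the other per-group reading.** If the gate were a two-sided paired t-test against zero within each group at d = 0.48, power would be 48% with n = 18 and 53% with n = 20. The plan does not propose this test. The figures show only that this reading does not rescue the sentence either.

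**The case against.** The strongest reply is that the sentence is right on its own terms. Power to detect a difference ordinarily means a test against zero, and for the pooled sample the figure reproduces to rounding. Any cutoff on an observed mean is passed half the time when the truth lies on it. The plan expects at least d = 0.68, where each group passes about 80% of the time.

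Much of this stands. The Aim 1 calculation contains no arithmetic error, and the 50% figure is not a design flaw. What does not stand is the placement. Attached to the gate, and referring to the 7.2-point difference, the figure describes neither the gate's rule nor the unit to which the dose rule applies it.

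Three stronger readings are tempting but unsupported:

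- **That release of R33 is unreliable.** At the expected effect, at least one group passes about 96% of the time under the stated assumptions.
- **That the plan leaves open whether release is pooled or by group.** The provision that a single passing group supplies the R33 dose already implies that one passing group is enough to proceed.
- **That the power sentence causes dose selection by chance.** That possibility comes from the dose rule, which the plan is free to choose and which correcting the sentence leaves unchanged. The plan also says openly that dose selection does not require statistical significance.

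**Conclusion.** The point holds as a misattributed power statement that should be corrected. At the 7.2-point drop to which the sentence refers, the gate passes 50% of the time per group and 75% for at least one group, and neither reaches 80%. These two figures do not depend on SD or n. The 75% also assumes the same true drop in two independent groups.

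At the expected effect the practical consequence for release is small. The figure most worth showing is the chance of about 32% that exactly one group passes although both have the same true effect, which is the situation the plan itself expects for last-session dwell time. In that event the LSAS step is never reached. This figure is conditional on SD 15, a 10.2-point drop and n = 18, and it moves between 7% and 36% over the inputs examined.

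That the sentence derives from Aim 1 is an inference, since the plan does not define its scenarios. It rests on the exact match at d = 0.48 and on the absence of any other dwell-time power calculation in the text reviewed.

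**What to change.** In the R61 Go-Nogo Criterion, delete the sentence claiming more than 80% power, or attribute it expressly to the whole-sample Aim 1 analyses, with the wording 'about 80%' for the completer test. In its place, give the gate's per-group, at-least-one and exactly-one pass probabilities, each labelled with the assumed true drop, SD and n. A short table for d = 0.48, 0.68, 0.80 and 0.90 and SD 10 to 18 would do.

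The cost is one sentence and one small table. Sample size, procedures, the release rule and the dose rule do not change. The downside is that the figure stated beside the gate becomes less favourable.

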### 3.3. C. Research Design and Methods: R61 Phase.

**3.3. C.1. Overview.** The R61 Phase is designed to clarify engagement of the attention allocation target, to optimize dosage of GC-MRT (RCT comparing 8 vs. 12 sessions), and to explore whether the treatment engages two processes influencing attention allocation: disengagement from threat, and social reward.

**3.3. C.2. R61 Method: Patients:** The goal is to enroll a sample with clinically significant SAD, using few exclusion criteria to maximize generalizability. Patients will be obtained by clinical referral and recruitment notices posted online and locally. Forty adults age 18-60 with clinically significant SAD, as assessed by MINI structured interview and self-rated Liebowitz Social Anxiety Scale (LSAS-SR) total  $\geq 50$ , will enter the study after psychiatric clinical evaluation, including and Hamilton Rating Scale for Depression (HRSD). The LSAS cutoff score was chosen for optimal balance between diagnostic specificity and sensitivity for SAD. Key exclusion criteria will be at least moderately severe depression (HDRS 17-item score  $>20$ ), indicating greater need for non-experimental treatment; substance use disorder in the past 30 days (other than nicotine, or mild alcohol or cannabis abuse); bipolar or psychotic disorders; acute suicidal ideation (assessed by Columbia Suicide Severity Rating scale, CSSR); other unstable psychiatric, neurological, or medical conditions that could interfere with study participation or interpretation of outcomes; contraindication to MRI. (see Human Subjects for details).

[figure not shown]
The self-rated version of the LSAS will be used only at screening for eligibility assessment. The clinician-rated LSAS will be the primary outcome measure, assessed at baseline, during treatment, and post-treatment. Using the self-rated LSAS at screening avoids the bias that reportedly can occur when the primary outcome measure is the basis for an entry cutoff criterion, as raters could feel pressured to maximize baseline scores to meet the cutoff, thus distorting outcomes.

**3.3. C.3 R61 Intervention:** Patients will be randomized to 8 biweekly sessions of GC-MRT over 4 weeks vs. 12 sessions of GC-MRT over 8 weeks (8 biweekly, then 4 weekly), using GC-MRT as described above in the preliminary study, but without a control treatment – all R61 patients will receive active GC-MRT.

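### The R61 dose-selection rule ends by choosing an 8-session/12-week regimen that matches neither randomised arm; the session and week counts are transposed, here and in the analysis section's description of the extended arm

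*Combined protocol and SAP*

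**What the plan says.** Section 3.3. C.1 describes the R61 phase as an "RCT comparing 8 vs. 12 sessions". Section 3.3. C.3 defines the arms: a standard course of 8 sessions given twice weekly over 4 weeks, and an extended course of "12 sessions of GC-MRT over 8 weeks (8 biweekly, then 4 weekly".

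Section 3.3. C.5 restates the arms at the start of its R61 paragraph. The short arm is given correctly as "standard GC-MRT (8 sessions in 4 weeks", but the long arm appears as "extended GC-MRT (8 sessions in 12 weeks".

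The Go-Nogo criterion, later in the same section, refers to dwell time "during the last session of the 8-session or 12-session treatment". The dose-selection rule follows. If only one group passes, "that dose will be selected for the R33". If both pass, the test is whether LSAS improvement 8 weeks after starting treatment is at least 7 "points greater in the 12-session/8-week treatment group than in the 8-session/ 4-week treatment group". If it is, "we will use the 8-session/12-week treatment in the R33".

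**The concern.** The rule's condition and its consequence do not refer to the same regimens. The condition names the two randomised arms correctly. The consequence combines the short arm's session count with a duration of 12 weeks, which belongs to no arm defined in section 3.3. C.3.

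This sits in an operative, prespecified decision rule, and it is the only outcome the rule names when both groups pass. Under Aim 2 the plan says that dose selection does not depend on statistical significance and points the reader to this rule, so its wording is what governs the choice.

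Read literally, a better LSAS result with 12 sessions would send a different course into the R33: the same number of sessions as the arm that lost, over three times as long, with no R61 dwell-time or LSAS data behind it. A reader who matches on session count alone would be led to the losing arm itself. The repeat at the start of the R61 paragraph makes this worse, because someone who takes the arm definitions from the analysis section finds apparent support for the wrong label.

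**Working it through.** **The plan's own figure.** The one numerical result attached to the dose comparison is the Aim 2 minimum detectable effect, d = 0.96, with 18 completers per group and 80% power. A two-sample t-test (noncentral t) with n = 18 per group and alpha 0.05, assumed two-sided, gives d = 0.961 at 80% power, and 79.9% power at d = 0.96. The figure reproduces. It does not depend on how the arms are labelled, so nothing numerical changes with the correction.

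**Schedule of each regimen.** Inputs are from section 3.3. C.3, where biweekly must mean twice weekly, since 8 sessions fit into 4 weeks.

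- Standard arm: 4 weeks × 2 = 8 sessions in 4 weeks; 8/4 = 2.0 per week.
- Extended arm: (4 weeks × 2) + (4 weeks × 1) = 12 sessions in 4 + 4 = 8 weeks; 12/8 = 1.5 per week.
- Regimen named at the end of the rule: 8 sessions in 12 weeks; 8/12 = 0.67 per week.

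The named regimen has 12 − 8 = 4 fewer sessions than the extended arm and runs 12 − 8 = 4 weeks longer. Its average rate is 0.67/1.5 = 44% of the extended arm's and 0.67/2.0 = 33% of the standard arm's. Its session count equals the standard arm's, and its duration is 12/4 = 3 times as long.

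**All statements of the extended regimen, side by side.**

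| Place | Sessions | Weeks | Agrees with C.3? |
|---|---|---|---|
| C.1 Overview | 12 | – | yes |
| C.3 Intervention | 12 | 8 | (definition) |
| C.5, start of R61 paragraph | 8 | 12 | **no** |
| C.5, Aim 2, Hypothesis 2 | – | 8 | yes |
| C.5, Aim 2, power analysis | – | 8 | yes |
| C.5, Go-Nogo criterion | 12 | – | yes |
| C.5, dose rule, condition | 12 | 8 | yes |
| C.5, dose rule, outcome | 8 | 12 | **no** |
| Protection of Human Subjects, Overview | 12 | – | yes |

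Two of nine are wrong, both by the same transposition. Of the four that give both sessions and weeks, two are right and two are wrong.

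**Could 8 sessions in 12 weeks be the real design?** No. The clinical assessments in sections 3.3. C.4 and C.4.d fall at weeks 0, 2, 4 and 8 and at 3-month follow-up, and Aim 2 tests LSAS 8 weeks after starting treatment. A 12-week course would still be running at week 8, and no week-12 post-treatment visit is listed. The rule's preceding sentence also limits the candidates to the doses tested.

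**The case against.** The strongest reply is that the same sentence resolves the slip. It names both candidate arms correctly, and its condition is that the longer course wins by the margin, so the only sensible consequence is to use the longer course. Patients are treated to the schedule in section 3.3. C.3, which is explicit. The comparison, the 7-point margin and the time point are unaffected, and no analysis or power figure depends on the label. On this view the sessions-per-week figures measure a regimen nobody expects to deliver, and the two-in-nine count mixes full and partial statements.

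Most of this stands, and it settles the severity. The intent is recoverable, the count is not a like-for-like error rate, and the rate arithmetic describes only the literal reading. It is also fair that the start of the R61 paragraph, read alone, would define an 8-session/12-week arm; the accurate statement is that two phrases conflict with the intervention section, which should control. None of this makes the text correct. A prespecified rule should name the regimen it selects, and this one names a different regimen.

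**Conclusion.** The inconsistency is real and minor. As written, the rule selects a regimen that section 3.3. C.3 does not assign to anyone, and the analysis section's description of the extended arm carries the same error. This rests on taking section 3.3. C.3 as the controlling definition, which the other correct statements and the assessment schedule support. The effect is confined to labels: no sample size, power figure or analysis changes, and R61 conduct is not expected to differ.

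**What to change.** In section 3.3. C.5, make two edits:

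1. At the end of the dose-selection rule, replace the label 8-session/12-week with 12-session/8-week.
2. At the start of the R61 paragraph, describe the extended arm as 12 sessions in 8 weeks.

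Both should be made together, since correcting only one leaves a conflict within the section. The cost is two phrases, with no redesign or recalculation. This corrects labels only. What happens when both groups pass and the LSAS difference is below 7 points is a separate matter that these edits do not address.
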